5.2.1 Diagnostic Tests, Scales, Measures, etc.	9
5.3 SAFETY EVALUATION	9
5.4 PRIMARY ENDPOINT	9
5.5 SECONDARY ENDPOINTS	9
5.6 STATISTICAL METHODS.....	10

5.6.1	Baseline Data	10
5.6.2	Efficacy Analysis	10
5.7	SAMPLE SIZE AND POWER	11
6	STUDY MEDICATION (STUDY DEVICE OR OTHER STUDY INTERVENTION)	14
6.1	DESCRIPTION	14
7	SAFETY MANAGEMENT	14
7.1	CLINICAL ADVERSE EVENTS	14
7.2	ADVERSE EVENT REPORTING.....	14
8	STUDY ADMINISTRATION	14
8.1	TREATMENT ASSIGNMENT METHODS.....	14
8.1.1	Randomization	14
8.1.2	Blinding	15
8.2	DATA COLLECTION AND MANAGEMENT	15
8.3	CONFIDENTIALITY	20
8.4	REGULATORY AND ETHICAL CONSIDERATIONS.....	20
8.4.1	Data and Safety Monitoring Plan	20
8.4.2	Risk Assessment	20
8.4.3	Potential Benefits of Trial Participation	20
8.4.4	Risk-Benefit Assessment	20
8.5	RECRUITMENT STRATEGY	21
8.6	INFORMED CONSENT/ASSENT AND HIPAA AUTHORIZATION	21
8.6.1	Partial Waiver/alteration of HIPAA Authorization	21
8.6.2	Waiver of Consent	22
8.7	PAYMENT TO SUBJECTS/FAMILIES.....	24
9	PUBLICATION	24
10	REFERENCES	25

ABBREVIATIONS AND DEFINITIONS OF TERMS

AE	Adverse event
API	Application Programming Interface
App	Mobile application
BTE	Bluetooth Low Energy
cACT	Child Asthma Control Test
CHOP	Children's Hospital of Philadelphia
CSV	Comma Separated Values
DHS	Department of Human Services
DMS	Data Management System
ED	Emergency Department
FDA	Food and Drug Administration
HAU	Healthcare Analytics Unit
ICS	Inhaled Corticosteroids
ID	Identification
PII	Personal Identifiable Information
PMACS	Penn Medicine Academic Computing Services
SAE	Serious Adverse Event
SQL	Structured Query Language
UPenn	University of Pennsylvania
WTH	Way to Health

ABSTRACT

Context: (Background)

Poor adherence to inhaled corticosteroid (ICS) medications for children with high risk asthma is a well-documented and poorly understood problem with a disproportionate prevalence and impact on urban minority children. Financial incentives have been shown as a compelling method to engage a high-risk asthma population in regular ICS use, but whether and how adherence can be maintained and lead to sustained high adherence trajectories is unknown.

Objectives: (primary and important secondary objectives)

- 1) Determine the marginal effects of financial ICS incentives on adherence (1° outcome) and healthcare system use and costs (2° outcomes) in a prospective cohort of child-caregiver dyads.
- 2) Assess proposed mechanisms by which intervention strategy influenced adherence trajectory, including (1) participant self-efficacy, (2) medication responsibility, and (3) habit formation.
- 3) Explore caregiver and child perceptions of acceptability of intervention components and how they influenced adherence trajectory.

Study Design:

Basic design: Randomized controlled trial

Setting/Participants:

To accomplish the above objectives, we propose to enroll 125 children and their parents in a six-month intervention with a six-month follow-up period. Children will be ages 5-12, and must have two or more visits to any combination of the outpatient, ED or hospital setting in the past year for asthma exacerbations at Children's Hospital of Philadelphia.

Study Interventions and Measures:

[figure not shown]
The study intervention will include daily automated medication reminders (either via text message or push reminder), an app to track daily medication use, and nominal incentives to promote daily controller use. Inhaled controller medication adherence and rescue medication use will be measured using electronic monitors affixed to the inhalers. Factors associated with differential adherence will be assessed using surveys administered during enrollment, the experiment interval (months 2 and 4), the observation interval (month 7), and study completion (months 12-13). Efficacy outcomes will include change in parent-reported asthma control and mean adherence to ICS between study arms during the experiment interval, as well as the observation interval.

TABLE 1: SCHEDULE OF STUDY PROCEDURES

Study Phase	Screening and initial survey	Run-in period	Study survey	Experiment period			Study survey	Observation period	Study survey	Study completion survey
Visit Number	1 (clinic/hospital/phone)		2 (clinic/phone)				3 (clinic/phone)		4 (clinic/home phone)	5 (clinic/phone)
Arms	1,2,3	1,2,3	1,2,3	1	2	3	1,2,3	1,2,3	1,2,3	1,2,3
Study Month	0	0	2	1-3			4	4-6	7	12-13
Informed Consent/Assent	X									
Review Inclusion/Exclusion Criteria	X									
Demographics/Medical History	X									
Prior/Concomitant Medications	X									
Dispense Electronic Monitors	X									
Questionnaires	X		X				X		X	X
Child asthma control tool	X		X				X		X	X
Electronic monitoring		X		X	X	X		X	X	X
Daily medication reminders				X	X					
Adherence incentives				X						

FIGURE 1: STUDY DIAGRAM

A flow diagram of the study is included below.

1 BACKGROUND INFORMATION AND RATIONALE

1.1 Introduction

Poor adherence to asthma controller medications is a well-documented yet poorly understood problem. Despite compelling evidence demonstrating improved disease control, fewer exacerbations, and hospitalizations with regular use of ICS, adherence with prescribed regimens for inhaled corticosteroids in childhood asthma is approximately 50% of prescribed doses.¹ In urban minority populations, who suffer higher rates of morbidity and mortality from asthma, adherence estimates are even lower, ranging from 11 to 37%.²⁻⁵

1.2 Name and Description of Investigational Product or Intervention

The intervention will be a three-arm randomized control trial that assesses the effects of different strategies for withdrawing financial incentives for ICS use targeting a cohort of children with multiple asthma hospitalizations in the preceding year. The intervention leverages mobile health technology to provide a daily cue (reminder message) and reward (feedback message with performance-based incentives) designed to reinforce routine ICS use.

1.3 Selection of Drugs and Dosages

No new medications will be prescribed as part of this intervention. We will use an FDA-registered Class 1 device that affixes to most common inhalers to assess the use of currently prescribed ICS and rescue medication during the study interval.

1.4 Relevant Literature and Data

Improving adherence, particularly in high-risk populations, is challenging. Previous interventions to improve medication adherence have demonstrated effects that are modest, at best^{6,7}; thus, several emerging areas of study have catalyzed reinvestment in adherence interventions. First, technology-enhanced reminder systems have demonstrated robust ICS adherence improvements in other countries.⁸⁻¹⁰ Second, adult interventions infused with financial and social incentives from behavioral economics have enhanced behaviors as varied as medication adherence to smoking cessation.^{11,12} Few studies, however, have attempted to leverage mobile health technology and incentive design to improve medication adherence in children with high-risk asthma.

Two critical challenges limit the effectiveness of existing adherence interventions: (1) lack of knowledge of what it takes to engage high risk children and their caregivers, and (2) lack of enduring behavior change beyond the active intervention phase. Recent studies have begun to identify intervention components that tend to be more effective in engaging minority demographic groups¹³ and lead to sustained behavior change or habit formation.¹⁴ We recently conducted a pilot study of daily adherence reminders and feedback enriched with nominal financial adherence incentives (\$1/day for 30 days for perfect adherence) in families of children ages 5-11 with 3 asthma hospitalizations in the prior year. Study enrollment (69%) and mean ICS adherence (80%) during the intervention month were robust; however, adherence dropped to 33% after incentives, reminders, and feedback ceased. These findings reveal that financial incentives are a compelling method to engage this high-risk asthma population in regular ICS use, but whether and how adherence can be maintained and lead to sustained high adherence trajectories is unknown in pediatric populations.

1.5 Compliance Statement

This study will be conducted in full accordance all applicable Children's Hospital of Philadelphia Research Policies and Procedures and all applicable Federal and state laws and regulations including 45 CFR 46. All episodes of noncompliance will be documented.

The investigators will perform the study in accordance with this protocol, will obtain consent and assent, and will report unanticipated problems involving risks to subjects or others in accordance with Children's Hospital of Philadelphia IRB Policies and Procedures and all federal requirements. Collection, recording, and reporting of data will be accurate and will ensure the privacy, health, and welfare of research subjects during and after the study.

2 STUDY OBJECTIVES

The purpose of the study is to automate a technology intervention to determine ICS adherence trajectories in children who are at high risk for asthma hospitalizations, identify potential mechanisms for adherence, and assess the efficacy and acceptability of the intervention among children and caregivers.

2.1 Primary Objective (or Aim)

The primary objective of this study is to determine the marginal effects of financial ICS incentives on adherence (1° outcome) and healthcare system use and costs (2° outcomes) in a prospective cohort of child-caregiver dyads.

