3 INVESTIGATIONAL PLAN

3.1 General Schema of Study Design

This is a three arm, randomized control trial study to assess the marginal effects of different strategies of financial incentives for ICS use targeting a cohort of children with high risk asthma.

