3.1.2 Run-in Phase (Month 0)

The study will be broken down into three discrete phases: (1) *Run-in* (2) *Experiment*, and (3) *Observation* (Figure 2). During the *Run-in* phase, every caregiver-child dyad will have access to the inhaler sensor app and will receive electronic ICS use monitoring. ICS use will be monitored using an electronic sensor that affixes to their ICS inhaler and will remain through the study *Observation* phase. Participants will be sent 4 text messages, each designed to elicit a response from the caregiver about the study technology or the study itself. (See Appendix 1 for content of the Run-in text messages) Participants for whom any inhaler use data is transmitted to the study platform within the first 2 weeks of the Run-in Phase AND reply to one or more of the 4 text messages sent from the study platform (“Responders”) will be randomized into one of three arms at the end of the Run-in phase. (see section 4.10 for details on procedures for “Non-responders”) The second two weeks of the Run-in Phase is designed to provide baseline adherence data.

[figure not shown]

Figure 2: Study schema for proposed RCT

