3.1.3 Experiment Phase (Months 1-3) and Observation Phase (Months 4-6)

The three experimental conditions will be: financial incentives, adherence reminders, and feedback (Arm 1); adherence reminders and feedback without incentives (Arm 2); or electronic monitoring alone (Arm 3). The financial incentives in Arm 1 will consist of 3 months of fixed-ratio incentives for each ICS actuation (i.e. 25 cents per puff for children on 4 daily ICS doses and 50 cents per puff for children on 2 daily doses), with a maximum of \$1 per day. With regard to the reminders and feedback in Arms 1 and 2, study participants will receive automated daily text message or push notification reminders and automated weekly feedback summarizing their adherence performance through Way to Health, a mobile health, electronic monitoring platform (described below in section 4.1). At the end of the first month of the experiment phase, families will be contacted by study staff to complete a follow-up survey that will reassess disease control, medication supply, and intentions and behaviors with

regard to ICS use (study visit 2). After the experiment interval, families will be contacted again by study staff to complete a follow-up survey and a semi-structured interview (study visit 3). At this point, all reminders, feedback, and incentives will cease, but daily ICS use monitoring will continue with the electronic sensors for all study arms (*Observation* phase) to assess for enduring effects. There will be a fourth study visit in the 7th study month, when study surveys will be completed, and a fifth and final study visit at one year assessing asthma control and health care utilization outside of the CHOP system.

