4.14 Primary Endpoint

The primary outcome will be adherence to ICS regimen both during the *Experiment* interval (months 1-3). Adherence over these study intervals will be characterized as a daily observed-to-prescribed ICS adherence proportion averaged by study month. To operationalize this, a daily medication use log composed of 180 sequential ICS use observations will be generated, representing the count of ICS doses taken each day of study enrollment. These daily counts will be converted into proportions by dividing by the daily prescribed dose and imposing an upper limit of 1 in order to prevent doses taken above the prescribed limit – either during the use of flare plans or attempted “gaming” of the incentives by the participants – from influencing interval adherence estimates. Observed actuations will be quantified using electronic sensors.

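### Section 4.16.2 puts the run-in month into the primary outcome (months 0-3 instead of 1-3) and names no primary contrast; the stated objective also does not match the powered comparison

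*Combined protocol and SAP*

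**What the plan says.** **Objective.** Section 2.1: "The primary objective of this study is to determine the marginal effects of financial ICS incentives on adherence". The Abstract has the same: "Determine the marginal effects of financial ICS incentives on adherence". Two other sections word the aim differently: 1.2 says the trial "assesses the effects of different strategies for withdrawing financial incentives for ICS use", and 3.1 says it is designed "to assess the marginal effects of different strategies of financial incentives for ICS use".

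**Arms.** Section 3.1.3 lists "financial incentives, adherence reminders, and feedback (Arm 1); adherence reminders and feedback without incentives (Arm 2); or electronic monitoring alone (Arm 3".

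**Timing.** Section 3.1.2 makes month 0 the run-in. Responders "will be randomized into one of three arms at the end of the Run-in phase", and "The second two weeks of the Run-in Phase is designed to provide baseline adherence data".

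**Primary outcome.** Section 4.14 places it in the Experiment "interval (months 1-3). Adherence over these study intervals will be characterized as a daily observed-to-prescribed ICS adherence proportion averaged by study month". The primary-analysis paragraph of 4.16.2 instead gives months 0-3 and calls that span the Experiment phase. It specifies a GEE with arm, month and their interaction, reserves an arcsine transformation, states no link function, and names no arm comparison as the primary test.

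**Power.** Section 4.17 sizes the trial for Arm 1 versus Arm 3 on average Experiment-phase adherence (65% versus 35%, 40 per arm, 50 after 20% loss). It says that Arm 1 versus 2 and Arm 2 versus 3 are not powered and will yield preliminary estimates of the component effects.

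**The concern.** The sample-size section implies one primary test, but the analysis section does not carry it over. With an arm-by-month interaction, the arm effect could mean the difference in a single month, a joint test over months, or an average over months. These are different hypotheses, and the choice is left open until data exist.

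The outcome window makes this worse. Month 0 precedes all arm-specific treatment, so the arms are expected to be equal in it. Treated as an outcome month, it pulls the estimated effect towards zero. Treated as the reference month, it turns the arm coefficient into a comparison of arms before treatment.

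Separately, the objective promises an answer about incentives, while the powered comparison changes incentives, reminders and feedback together. A positive Arm 1 versus Arm 3 result could be reported as meeting an objective that it cannot isolate.

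**Working it through.** **1. The window, side by side**

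| Place | Window |
|---|---|
| Table 1 | Run-in at month 0, Experiment 1-3, Observation 4-6 |
| 3.1.2 | Month 0 is the run-in; randomization at its end |
| 3.1.3, 4.4 | Experiment phase is months 1-3 |
| 4.14 | Primary outcome in months 1-3; daily log of 180 observations |
| 4.16.2 | Primary outcome in months 0-3; secondary in 4-6 and 7-13 |

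The log length agrees with the majority. With the 30-day month that 3.1.3 uses for incentives, 180/30 = 6 months, which fits months 1-6. Adding month 0 would need 210. Section 7.1.1 also mentions assignment at enrolment, but 4.4 says families do not learn their arm until the Experiment phase begins, so month 0 carries no arm-specific treatment either way.

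**2. The plan's own sample size**

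Two proportions, unpooled variance, two-sided 0.05, 80% power:

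n = (1.960 + 0.842)² × (0.65×0.35 + 0.35×0.65) / 0.30² = 7.85 × 0.455 / 0.09 = 39.7, so 40 per arm. Then 40/0.8 = 50 enrolled.

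The figure reproduces, but from a binary formula. No SD of mean adherence is given. The binary variance corresponds to an SD of √(0.65×0.35) = 0.477; SDs of 0.25 and 0.35 below are assumptions.

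**3. If month 0 is averaged in as an outcome**

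Diluted difference: (0 + 30 + 30 + 30)/4 = 22.5 points.

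*Plan's binary variance, taken as unchanged.* SE = √(0.455/40) = 0.1067. Power at 30 points: Φ(0.30/0.1067 − 1.96) = Φ(0.85) = 80%. At 22.5 points: Φ(0.225/0.1067 − 1.96) = Φ(0.15) = 56%.

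*Means, two-sample t, 40 per arm.* Averaging four months instead of three changes the SD by the factor √{[(1+3ρ)/4] / [(1+2ρ)/3]}, where ρ is the between-month correlation. This is 0.968 at ρ = 0.5 and 0.996 at ρ = 0.9.

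| SD of 3-month average | Power, months 1-3, 30 points | Power, months 0-3, 22.5 points |
|---|---|---|
| 0.25 | over 99% | 98% |
| 0.35 | 97% | 84% (ρ = 0.5) to 81% (ρ = 0.9) |
| 0.477 (binary, unchanged) | 80% | 56% |

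**4. If month 0 is only a baseline row**

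With Arm 3 and month 0 as reference levels, the Arm 1 coefficient is the Arm 1 minus Arm 3 difference in month 0, which is zero in expectation. The treatment effect lies in the interactions: its average over months 1-3 is the Arm 1 coefficient plus one third of the sum of the three Arm 1-by-month coefficients. There is no dilution, but a reader who tests the arm main effect tests the wrong quantity.

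**5. The contrast that isolates incentives, Arm 1 versus Arm 2**

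With 20% loss this is 40 versus 20 children.

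- Binary variance, 30 points: SE = √(0.65×0.35/40 + 0.35×0.65/20) = 0.1306; power = Φ(0.30/0.1306 − 1.96) = 63%. For an assumed 15 points (65% versus 50%), power is 20%.
- Means at SD 0.25 to 0.35: 95% CI half-width 1.96 × SD × √(1/40 + 1/20) = 13 to 19 points; smallest difference detectable with 80% power, 20 to 27 points; power for 15 points, 58% to 34%.

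**The case against.** The strongest reply is that months 0-3 is a slip, or that month 0 is meant as a baseline row. Every other section says months 1-3, 3.1.2 calls part of the run-in baseline data, and the interaction terms would then carry the treatment effect. Nothing in the plan prescribes averaging over months 0-3 or testing the arm main effect. This stands as far as the dilution goes: the loss of power is conditional. It does not remove the conflict, because 4.16.2 calls those months the primary outcome and labels all of them Experiment phase. Nor does it supply the missing contrast. Reading 0-3 as elapsed time fits poorly, since the same paragraph continues with 4-6 and 7-13, which count study months.

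A reader might infer three stronger things that the documents do not support:

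- *That the plan hides its lack of power for incentives alone.* Section 4.17 states it and gives it as the reason for 2:1:2 allocation. This is a legitimate, disclosed choice; what remains is a mismatch between determining an effect (2.1) and estimating it preliminarily (4.17).
- *That 4.16.2 never compares Arm 1 with Arm 3.* Its secondary analysis does, but on trajectory group and not on mean adherence.
- *That the trial would fall below its 80% target.* Even with month 0 averaged in, power stays at 81% or more for SDs of 0.25 to 0.35. It falls below target on the binary variance that produced the 40 per arm.

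**Conclusion.** The point holds in a limited form. Section 4.16.2 contradicts four other places on the primary outcome window and leaves the primary adherence test unnamed. Both should be settled before the data are analysed.

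The size depends on how month 0 is used. Averaged in, it cuts any constant effect in months 1-3 by a quarter. The cost in power runs from negligible (SD 0.25) to about 24 percentage points (binary variance, assumed unchanged). Used as a baseline row, it costs no power but makes the arm main effect uninformative about treatment. The SDs and the between-month correlations are assumptions.

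The wording of the objective is the lesser issue: Arm 1 versus Arm 3 supports a claim about the package, not about incentives on their own.

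**What to change.** 1. **Window.** In 4.16.2, change the primary outcome to months 1-3. Use only months 1, 2 and 3 as outcome rows, and enter adherence in the second two weeks of run-in as a baseline covariate. Randomization requires data only from the first two weeks, so state how randomized children with none in the second two weeks stay in the analysis, for example by a missing-baseline indicator or simple imputation.
2. **Contrast.** Name the primary test: Arm 1 minus Arm 3 in the equally weighted average of months 1-3, two-sided 0.05, estimated on the untransformed proportion scale (identity link), with any arcsine analysis as a sensitivity check. With Arm 3 and month 1 as reference levels, this is the Arm 1 coefficient plus one third of the sum of its month 2 and month 3 interaction coefficients.
3. **Objective.** Reword 2.1 and the Abstract so that the primary objective is the effect of the combined package (adherence-contingent incentives, reminders and feedback) versus electronic monitoring without these, on adherence in months 1-3. Say adherence-contingent, because Arms 2 and 3 also receive $10 a month for any recorded actuation. Keep healthcare use and costs as secondary outcomes, report Arm 1 versus 2 and Arm 2 versus 3 as exploratory estimates with 95% CIs, and align 1.2 and 3.1, since no arms compare incentive or withdrawal strategies.

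**Cost.** A small change to the primary model specification plus wording, and a narrower headline claim about incentives. Arms, sample size and data collection do not change. It is best done while the statistics team is blinded (7.1.2). The alternative, making Arm 1 versus Arm 2 primary, would need 45 to 87 evaluable children per arm for an assumed 15-point effect at SD 0.25 to 0.35 (45/0.8 and 87/0.8, so 57 to 109 enrolled), against 50 and 25 planned.

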2.2 Secondary Objectives (or Aim)

The secondary objectives are to:

- Automate intervention delivery by developing a closed loop for electronic monitoring of ICS inhaler use and adherence incentive feedback.
- Assess proposed mechanisms by which intervention strategy influenced adherence trajectory, including (1) participant self-efficacy, (2) medication responsibility, and (3) habit formation.
- Explore caregiver and child perceptions of acceptability of intervention components and how they influenced adherence trajectory.

